11.1 Demographics

Summaries will be given for the safety, the pharmacokinetic set, and pharmacodynamic set, if different.

Demographic characteristics will be listed by subject and summarized using the following information from the Screening/Baseline Visit CRF pages.

Demographic characteristics:

- Sex: female (only females included in this trial)
- Race: Black or African American, American Indian or Alaska Native, Asian, Native Hawaiian or other Pacific Islander, White, Other
- Ethnic origin Hispanic or Latino: yes, no
- Ethnic origin Japanese: yes, no
- Age (years): summary statistics
- Height (cm) at Baseline: summary statistics
- Weight (kg) at Baseline: summary statistics
- BMI (kg/m²) at Baseline: summary statistics

Age will be taken from the CRF and cannot be derived from the data because only the year of birth is collected in the CRF.

BMI will be re-derived (ie, not taken directly from the database) according to the following formula:

• BMI (kg/m^2) = weight (kg) / (height (m) * height (m))

11.2 Medical History

The medical history will be listed by subject including the preferred term and MedDRA system organ class (SOC) body using MedDRA, current version.

11.3 Other Baseline Characteristics

Other baseline characteristics will be listed by subject and summarized using the following information from the Screening/Baseline Visit CRF pages.

Other baseline characteristics:

- Smoking status
- Alcohol consumption

12 Previous or Concomitant Medications/Procedures

Previous medications are medications, other than trial medications and pre-medications for trial drug, which started and stopped before first administration of trial drug.

Concomitant treatments are medications, other than trial medications, which are taken by subjects any time on-trial (on or after the first day of trial drug treatment for each subject).

In case the date values will not allow to unequivocally allocating a medication to previous or concomitant medication the medication will be considered as concomitant medication

Any previous and concomitant medication will be encoded with WHO-DD, latest version. Prior and concomitant medications will be listed by subject (all subjects).

The following information will be displayed in a listing: generic or trade name (as reported in CRF), WHO drug name (including coding), dose/unit, route, frequency, reason for use, start/end date and time.

Concomitant procedures will be presented in a data listing.

13 Treatment Compliance and Exposure

A listing of date and time of each drug administration and each blood sampling including time deviations will be provided sorted by subject.

14 Efficacy Analyses

Not applicable.

15 Safety Analyses

The subsections in this section include specifications for summarizing safety endpoints that are common across clinical trials such as adverse events, laboratory tests and vital signs.

Safety data analysis will be conducted on the Safety Analysis Set.

15.1 Adverse Events

All adverse events will be summarized overall as well as by Run-in period and per treatment sequence by period, Microgynon alone, Microgynon + Cladribine, Microgynon + Placebo and overall.

For subjects assigned to treatment sequence 1, cladribine-placebo (see also Section 1.2 of the study protocol), the following treatment labels will be used in tables and listings:

- Run-in Period: From run-in period until Day 1 of period 1, pre-dose to Microgynon
 - In case of missing AE time on Day 1 of run-in period, the AE will be assigned to Run-in Period.
- Microgynon alone: From Day 1 of period 1, post-dose to Microgynon until Day 9 of period 1, pre-dose of Cladribine
 - o In case of missing AE time on Day 1 of period 1, the AE will be assigned to Microgynon alone
- Microgynon + Cladribine: From Day 9 of period 1, post-dose to Cladribine until Day 1 of period 2, pre-dose of Microgynon
 - In case of missing AE time on Day 9 of period 1, the AE will be assigned to Microgynon + Cladribine
 - In case of missing AE time on Day 1 of period 2, the AE will be assigned to Microgynon + Cladribine
- Microgynon alone: From Day 1 of period 2, post-dose to Microgynon until Day 9 of period 2, pre-dose of Placebo
- Microgynon + Placebo: From Day 9 of period 2, post-dose to Placebo until Day 15 of period 2, pre-dose of Cladribine
 - In case of missing AE time on Day 9 of period 2, the AE will be assigned to Microgynon + Placebo
- Microgynon + Cladribine: From Day 15 of period 2, post-dose to Cladribine until end of study.
 - In case of missing AE time on Day 15 of period 2, the AE will be assigned to Microgynon + Cladribine

Object No.

Global Version ID:

For subjects assigned to treatment sequence 2, placebo-cladribine, the following treatment labels will be used in tables and listings:

- Run-in Period: From run-in period until Day 1 of period 1, pre-dose to Microgynon
 - In case of missing AE time on Day 1 of run-in period, the AE will be assigned to Run-in Period.
- Microgynon alone: From Day 1 of period 1, post-dose to Microgynon until Day 9 of period 1, pre-dose of Placebo
 - In case of missing AE time on Day 1 of period 1, the AE will be assigned to Microgynon alone
- Microgynon + Placebo: From Day 9 of period 1, post-dose to Placebo until Day 1 of period 2, pre-dose of Microgynon
 - In case of missing AE time on Day 9 of period 1, the AE will be assigned to Microgynon + Placebo
 - In case of missing AE time on Day 1 of period 2, the AE will be assigned to Microgynon + Placebo
- Microgynon alone: From Day 1 of period 2, post-dose to Microgynon until Day 9 of period 2, pre-dose of Cladribine
 - Microgynon + Cladribine: From Day 9 of period 2, post-dose to Cladribine until end of study. In case of missing AE time on Day 9 of period 2, the AE will be assigned to Microgynon+Cladribine

The number and percentage of subjects experiencing at least one TEAE will be summarized by treatment as well as the number of events. A TEAE is an AE with onset after start of treatment. Start of treatment defines the minimum date of first intake of microgynon or cladribine or placebo. Tables by relationship to trial drug and by severity will be generated. AEs will be coded using Medical Dictionary for Regulatory Activities terminology, latest version.

If an event was reported more than once, the worst severity will be tabulated.

Incomplete TEAE-related dates will be handled as follows:

- In case the onset date is missing completely or missing partially but the onset month and year, or the onset year are equal to the start of trial treatment then the onset date will be replaced by the minimum of start of trial treatment and TEAE resolution date.
- In all other cases the missing onset day or missing onset month will be replaced by 1.

- Incomplete stop dates will be replaced by the last day of the month (if day is missing only), if not resulting in a date later than the date of subject's death. In the latter case, the date of death will be used to impute the incomplete stop date.
- In all other cases the incomplete stop date will not be imputed.

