4.1 Overall Design

This is a randomized, double-blind, 2-period, 2-sequence crossover study with a 1 month Run-in-Period in pre-menopausal women with active relapsing multiple sclerosis (RMS) requiring a disease-modifying RMS treatment. The overall study design is shown in Section 1.2, Figure 1.

The study design will comprise a ≤ 21 -day Screening period followed by a Microgynon Run-in-Period, followed by 2 sequential treatment periods (Study Periods 1 and 2) of 28 days each.

In case the Screening period lasts > 21 days and ≤ 60 days due to a delayed menstrual cycle of the participant (Run-in Day 1), it is acceptable that the participant starts with a delayed Run-in-Period without having re-performed the Screening assessments (in order to minimize unnecessary investigational burden for the participant). In case of the requirement to re-assess one or more Screening laboratory value(s), the Screening period may be prolonged for up to 8 weeks after the last Screening laboratory assessment and it is acceptable that the participant starts with a delayed Run-in-Period without re-assessing the complete set of Screening laboratory assessments. In both cases, the participant does not need to sign a new Informed Consent Form (ICF).

In the Run-in-Period as well as during both treatment periods, Microgynon (1 tablet/day containing 30 μg ethinyl estradiol [EE] and 150 μg levonorgestrel [LNG]) will be administered for 21 days, followed by 7 days off-treatment. In Study Periods 1 and 2 Microgynon will continue to be administered together with randomized treatment sequences of a 5-day once-daily cladribine 10 mg tablet treatment (Day 9 to Day 13 of Study Period 1) followed by a 5-day once-daily matched placebo treatment (Day 9 to Day 13 of Study Period 2) or vice versa; i.e., participants will be randomized to 1 of 2 double-blind treatment sequences, either cladribine-placebo or placebo-cladribine. Additionally, matched placebo treatment (Day 15 to Day 19) will be given in order to protect the blind for the cladribine-placebo sequence, that will receive their second weekly dose of cladribine on Day 15 to Day 19 in Study Period 2. In turn, the placebo-cladribine sequence will receive the second weekly dose of cladribine after the End of Study Visit as part of standard medical care.

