Participants randomized to the treatment sequence placebo-cladribine, will receive their first 5-day cladribine treatment in Study Period 2 (Days 9 to 13), and will receive their second 5-day cladribine treatment between 28 to 35 days thereafter, which conforms to the approved cladribine posology. It is important to note, that this second cladribine treatment week will not be part of the study itself but provided as standard medical care of participants in the following month after end of the study (see Section 6.7).

Participants randomized to the treatment sequence cladribine-placebo, will receive their first 5-day cladribine treatment in Study Period 1 (Days 9 to 13). Since, according to the study design, they will have to receive Placebo treatment 4 weeks thereafter (i.e., Study Period 2, Days 9 to 13), their second 5-day cladribine treatment will have to be deferred by 6 days (i.e., Study Period 2, Days 15 to 19). Accordingly, participants will receive their second 5-day cladribine treatment 34 days after having received their first cladribine 5-day treatment in Study Period 1. This schedule will only marginally deviate from the approved cladribine posology. In view of the long-lasting duration of action of cladribine, this modest deferral of the second cladribine treatment week is unlikely to affect the overall efficacy of cladribine treatment.

The second cladribine treatment on Days 15 to 19 in Study Period 2 will not alter the primary study objectives, as the treatment is only initiated after all PK and  samples will have been taken on Day 14 with the last sampling in the morning of Day 15 (initiation of second cladribine treatment thereafter).

In order to also enable blinding of the Days 15 to 19 cladribine treatment in Study Period 2, all participants from both treatment sequences will receive placebo on Days 15 to 19 in Study Period 1, and participants randomized to the treatment sequence cladribine-placebo (Days 9 to 13) will receive cladribine on Days 15 to 19 in Study Period 2 as their second dose (see Section 1.2, Figure 1).

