8.2.4 Clinical Safety Laboratory Assessments

- Blood and urine samples will be collected for the clinical laboratory tests listed in Appendix 5, at the time points listed in the SoA (see Section 1.3). All samples should be clearly identified
- Additional tests may be performed at any time during the study, as determined necessary by the Investigator or required by local regulations
- The tests will be performed by the central laboratory with exception of the following tests done locally: Urine test for pregnancy and drug screening, QuantiFERON®-TB test
- The Sponsor must receive a list of the central laboratory normal ranges before shipment of study intervention(s). Any changes to the ranges during the study must be forwarded to the Sponsor or designated organization

- The Investigator must review each laboratory report, document their review, and record any clinically relevant changes occurring during the study in the AE section of the eCRF. The laboratory reports must be filed with the source documents
- Laboratory/analyte results that could potentially unblind the study will not be reported to investigative sites or other blinded personnel. Instead the medical monitor will review lymphocyte counts. Details are described in Section 6.9.
- Any abnormalities in any of the laboratory parameters will be judged by a physician individually in relation to the reference ranges from the laboratory. For all findings of clinical relevance, follow-up examinations will be carried out until the deviation returns to normal or the absence of pathological relevance can be confirmed
- For specific laboratory parameters such as lymphocyte count, however, that are reflecting a direct and long-lasting cladribine treatment effect, monitoring will follow the recommendations in the SmPC (Merck Serono Europe Ltd., 2017)
- In case of the requirement to re-assess one or more Screening laboratory value(s), the Screening period may be prolonged for up to 8 weeks after the last Screening laboratory assessment. From a participant safety perspective and in order to minimize unnecessary investigational burden for the participant it is acceptable that the participant starts with a delayed Run-in-Period of the study without re-assessing the complete set of Screening laboratory assessments. The participant does not need to sign a new ICF.

The laboratory parameters to be determined are provided in detail in [Appendix 5](#).

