- Is otherwise considered to be medically important. Important medical events that may not result in death, be life-threatening, or require hospitalization may be considered as SAEs when, based upon appropriate medical judgment, they may jeopardize the participant or may require medical or surgical intervention to prevent 1 of the outcomes listed above. Examples of such events include allergic bronchospasm requiring intensive treatment in an emergency room or at home, blood dyscrasias or convulsions that do not result in inpatient hospitalization, or the development of drug dependency or drug abuse.

For the purposes of reporting, any suspected transmission of an infectious agent via a study intervention is also considered an SAE, as specified below for reporting SAEs, AESIs (Adverse Event of special interest) and DLTs.

Events that Do Not Meet the Definition of an SAE

Elective hospitalizations to administer, or to simplify study intervention or procedures (e.g., an overnight stay to facilitate chemotherapy and related hydration therapy application) are not considered SAEs. However, all events leading to unplanned hospitalizations or unplanned prolongation of an elective hospitalization (i.e., undesirable effects of any administered treatment) must be documented and reported as SAEs.

Events Not to Be Considered as AEs/SAEs

Medical conditions present at the initial study visit that do not worsen in severity or frequency during the study are defined as Baseline Medical Conditions, and are not to be considered AEs.

Adverse Events of Special Interest

Description of selected adverse reactions

Lymphopenia

Only lymphopenia Grade 3 or Grade 4 represents AESIs. In clinical studies, 20% to 25% of the participants treated with a cumulative dose of cladribine 3.5 mg/kg over 2 years as monotherapy developed transient Grade 3 or 4 lymphopenia. Grade 4 lymphopenia was seen in less than 1% of the participants. The largest proportion of participants with grade 3 or 4 lymphopenia was seen 2 months after the first cladribine dose in each year (4.0% and 11.3% of participants with grade 3 lymphopenia in year 1 and year 2, 0% and 0.4% of participants with grade 4 lymphopenia in year 1 and year 2). It is expected that most participants recover to either normal lymphocyte counts or grade 1 lymphopenia within 9 months.

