15.3 Clinical Laboratory Evaluation

The following treatment labels will be used in tables and listings:

- Screening: During the screening period
- Run-in Period: During run-in period

- Microgynon + Placebo or Microgynon + Cladribine: For the measurement on Day 8, Day 9 and Day 14
- Follow-up: During follow-up/end of study period

All laboratory data will be reported with SI units. Laboratory parameters will be listed by subject and time-point and summarized indicating the treatment at the respective time-point using descriptive statistics and Box and Whisker plot for absolute values and change from baseline over time by treatment sequence, period and treatment.

Laboratory values that are outside the normal range will also be flagged in the data listings, along with corresponding normal ranges. Clinically significant abnormalities/outliers as per the Toxicity Grading Scale for Healthy Adult and Adolescent Volunteers Enrolled in Preventive Vaccine Clinical Trials will additionally be listed separately. Clinically significant values will be defined as values with toxicity grading of grade 2 or higher.

'Baseline' refers to the last scheduled measurement before administration of cladribine or placebo on Day 9 of each period. I.e. 'baseline' for period 1 refers to assessments on Day 21 of the run-in period.

Shift tables for post-dose shift (Low, Normal, High, Missing) will also be presented. The shift tables will be presented for follow-up versus screening.

See Appendix 5 of the clinical study protocol for a table of the safety laboratory evaluations.

Safety laboratory values are separated into:

- Hematology
- Biochemistry
- Urinalysis
- Other tests

Descriptive statistics shift tables and box plots will be created only for hematology and biochemistry results.

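### In the cladribine-placebo sequence, SAP 15.1 files Period 2 events that follow cladribine under *Microgynon alone* and *Microgynon + Placebo*

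*SAP*

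**What the plan says.** SAP 15.1 assigns each adverse event to a treatment label by its onset. In the cladribine-placebo sequence, *Microgynon + Cladribine* starts with the first cladribine dose on Period 1 Day 9 and stops at the first Microgynon tablet of Period 2. Two further labels follow before the second cladribine course starts on Period 2 Day 15. The first is *Microgynon alone*, which covers the eight days leading up to the placebo course. The second takes over once that course has begun: "Microgynon + Placebo: From Day 9 of period 2, post-dose to Placebo until Day 15 of period 2, pre-dose of Cladribine".

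The SAP has no label for time after a cladribine course. SAP 15.1 also summarises events per sequence by period. The TEAE tables in SAP 15.1.1 and the SAE table in SAP 15.2.2 count participants and events by treatment.

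SAP 15.3 labels laboratory values by the treatment of the current period: "Microgynon + Placebo or Microgynon + Cladribine: For the measurement on Day 8, Day 9 and Day 14". It resets baseline in each period to the last scheduled value before the Day 9 dose, which for Period 1 is Run-in Day 21.

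On persistence, Protocol 8.2.4 describes laboratory parameters such as lymphocyte count as ones "that are reflecting a direct and long-lasting cladribine treatment effect". Protocol 4.2 relies on cladribine's long duration of action to justify deferring the second course. Protocol Appendix 4, which makes Grade 3 or 4 lymphopenia the adverse event of special interest, states: "The largest proportion of participants with grade 3 or 4 lymphopenia was seen 2 months after the first cladribine dose in each year". It expects most participants to recover to normal or Grade 1 within 9 months.

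**The concern.** The labels treat the cladribine effect as over when the next Microgynon pack starts. No passage supports that cut-off, and the protocol's own account of lymphocyte depletion contradicts it for the one outcome it singles out for special reporting. In this sequence, every day after the first cladribine dose is cladribine-exposed in the sense that matters for delayed events.

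Safety and tolerability of co-administration is a secondary objective. A reader will naturally set the *Microgynon + Cladribine* column beside the other two. If events that arise three to five weeks after cladribine are counted in those other columns, the apparent difference shrinks, and a Grade 3 or 4 lymphopenia could be tabulated under placebo.

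**Working it through.** **Inputs**

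- Period length: Protocol 4.1 has a run-in "followed by 2 sequential treatment periods (Study Periods 1 and 2) of 28 days each".
- Cladribine-placebo sequence: first course on Period 1 Days 9 to 13, second on Period 2 Days 15 to 19 (Protocol 4.2).
- End of Study: 4 to 7 days after Period 2 Day 21 (Protocol 4.1).
- Label boundaries: SAP 15.1.
- Safety laboratory samples: Day 14 in Period 1, Days 9 and 14 in Period 2, and Run-in Day 21 as the Period 1 baseline (Protocol 1.3, SAP 15.3).

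**Reproducing the protocol's figures.** Continuous day = 28 × (period − 1) + day. The second course starts on 28 + 15 = 43 and the first on day 9; 43 − 9 = 34 days, as Protocol 4.2 states. The deferral is 43 − 37 = 6 days, also as stated.

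**Position of the two labels relative to the first course**

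| Point | Continuous day | Days after first dose (day 9) | Days after last dose (day 13) |
|---|---|---|---|
| Period 2 Day 1 | 29 | 20 | 16 |
| Period 2 Day 9 | 37 | 28 | 24 |
| Period 2 Day 14 | 42 | 33 | 29 |
| Period 2 Day 15 | 43 | 34 | 30 |
| End of Study | 53–56 | 44–47 | 40–43 |

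The *Microgynon alone* label covers days 20 to 28 after the first dose and *Microgynon + Placebo* covers days 28 to 34. Together they take 14 days, which is 14/47 to 14/44 = 30% to 32% of this sequence's on-study time after first cladribine.

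**Days under each label, per pair of completers (one per sequence)**

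| Label | Cladribine-placebo | Placebo-cladribine | Pair | Of the pair, after cladribine but not labelled so |
|---|---|---|---|---|
| Microgynon alone | 8 + 8 = 16 | 8 + 8 = 16 | 32 | 8 (8/32 = 25%) |
| Microgynon + Placebo | 43 − 37 = 6 | 29 − 9 = 20 | 26 | 6 (6/26 = 23%) |
| Microgynon + Cladribine | 20 + (10 to 13) = 30–33 | 16–19 | 46–52 | none |

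For the two reference labels together: 14/58 = 24%.

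**Laboratory values on Days 9 and 14.** Period 1 has no Day 9 safety sample. Placebo-labelled values per pair are therefore one from placebo-cladribine (Period 1 Day 14) and two from cladribine-placebo (Period 2 Days 9 and 14). Two of the three follow cladribine, by 28 and 33 days. The latest cladribine-labelled value is 14 − 9 = 5 days after the first dose in either sequence. The Period 2 baseline in cladribine-placebo, 28 days after the first dose, is itself post-cladribine.

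**The case against.** The strongest reply is that other displays already cover this. Adverse events are also shown per sequence by period. TEAEs are tabulated by relationship to MS treatment. AESIs and dosing times are listed by participant. Laboratory summaries in SAP 15.3 are split by sequence, period and treatment, and the laboratory shift tables compare follow-up with screening, so they do not depend on the label. A careful reader can therefore recover much of the picture. That stands, and it limits the point mainly to the TEAE and SAE tables by treatment. It does not remove the point. The relationship tables still use the treatment columns, and relatedness is generally judged by an investigator who is blinded and does not receive white cell counts after the run-in (Protocol 6.9).

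A second reply is that the labels merely record what was being taken. The SAP does not follow that rule. On Period 1 Days 15 to 19 all participants take placebo, yet in cladribine-placebo that time stays under *Microgynon + Cladribine*. The SAP already attributes some post-course time to cladribine.

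Four stronger readings are tempting, and the documents do not support them:

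- *The lymphocyte contrast reverses.* A reader might infer this from cladribine-labelled values at no more than 5 days and placebo-labelled values at 28 and 33 days. The documents give no lymphocyte time course over those days. The 2-month point in Appendix 4 lies beyond End of Study for a first course given in Period 1 (44 to 47 days).
- *Pooled laboratory columns are contaminated.* SAP 15.3 does not plan a summary pooled over sequence and period.
- *Vital signs and ECG need the same change.* No persistent effect on either is documented, and SAP 15.4 and 15.5 are already split by sequence and period.
- *The primary result is affected.* The bioequivalence analysis uses Day 14 profiles in a crossover ANOVA and does not depend on how adverse-event time is labelled.

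**Conclusion.** The point holds for the secondary safety reporting. In tables pooled by treatment label, about a quarter of the reference time per pair (23% of *Microgynon + Placebo*, 25% of *Microgynon alone*) follows in-study cladribine, so delayed events can be reported in the reference columns. For laboratory data, the label and the Period 2 baseline are the weak spots, not the layout of the summaries.

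The shares assume equal sequences, completers, nominal visit days, and by-treatment tables whose columns pool a label across sequences. They are shares of time, not of events. The documents give no event rate for days 20 to 34, so the size of any bias cannot be computed. Safety is analysed descriptively, so no test or estimated contrast is at risk. The change should be made before database lock, but it does not threaten the trial's main conclusion.

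**What to change.** - **SAP 15.1 and 15.3:** give cladribine-placebo Period 2, Day 1 to Day 15 predose, its own *after cladribine* label. Show it as a separate column in the by-treatment TEAE and SAE tables and in the AESI counts.
- **Reference time:** count only time before the first in-study cladribine dose as *Microgynon + Placebo* or *Microgynon alone*. It should be described in those words, because Protocol 6.5.2 and 6.5.3 admit second-year participants who have already had a full course.
- **Laboratory baseline:** add change from the Run-in Day 21 value for lymphocytes and the other haematology parameters in both periods. Relabelling alone would leave the cladribine-placebo Period 2 changes measured from a post-cladribine value.
- **Unchanged:** the sequence-by-period displays stay, and SAP 15.4 and 15.5 need no edit.

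The cost is SAP wording and programming, with no new data. Per pair, 14 days move to the new column, *Microgynon alone* falls from 32 to 24 days, and *Microgynon + Placebo* from 26 to 20. The drawback is that the clean placebo reference then comes only from the placebo-cladribine sequence, so comparison with cladribine becomes partly between participants in a small trial (16 evaluable for bioequivalence, Protocol 7.2). Keeping the existing displays beside it preserves the within-participant view.

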An End of Study examination will be performed within 4-7 days after the last visit of Study Period 2. To the extent possible, an Early Termination (ET) visit will be conducted for participants who withdraw prematurely. The same assessments as for the End of Study Visit will be conducted at the ET visit as far as feasible.

During the Run-in-Period participants will take Microgynon on an ambulatory basis and document daily drug intake in a participant diary. Participants will be requested to come to weekly visits in the mornings of Day 7, 14 and 21 for documentation of adverse events, participant diary check, and therapeutic drug monitoring (i.e., pharmacokinetic (PK) sampling for EE and LNG trough levels).

For Study Periods 1 and 2, participants will continue to take Microgynon on an ambulatory basis of Days 1 to 7 and to document drug intake in a participant diary. On Day 8 they will be hospitalized until discharge in the morning of Day 15 after completion of all in-house study-related assessments. At some study sites the hospitalization periods need to be conducted in

another location at so called Clinical Pharmacology study sites (PK-sites). For details regarding the study administrative structure and the complete coverage of Investigator responsibilities in case of a separate Investigational / PK site situation please see [Appendix 2](#) (Study Governance).

In individual cases Investigator may allow participants to stay overnight at home from Day 8 to 12. In this cases Investigator will provide participants with written instructions regarding the necessary compliance with lifestyle requirements.

Serial blood samples will be collected for the safety (hematology, biochemistry, coagulation), and the PK and CCI assessments to be performed throughout the residential part of each treatment period.

Participants will have to come for another ambulatory visit on Day 21 for documentation of adverse events, participant diary check, Microgynon medication collection and supply.

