8.2.1 Physical Examinations

Physical examination will be performed on the Screening Visit and on the End of Study Visit as scheduled in the Schedule of Assessments (see Section 1.3).

- A complete physical examination will include, at a minimum assessments of the Cardiovascular, Respiratory, Gastrointestinal and Neurological systems. Height (at Screen) and weight will also be measured and recorded. In addition, weight will be measured on Day 21 of Run-in-Period and Day 21 of Study Period 1 (to be able to calculate/adapt dosage of study intervention accordingly to actual weight) and Day 8 of Study Period 2.
- A brief physical examination will include, at a minimum, assessments of the skin, lungs, cardiovascular system, and abdomen (liver and spleen)
- Investigators should pay special attention to clinical signs related to previous serious illnesses.

Any relevant findings are to be recorded on the Medical History form in the eCRF (for findings from the past that occurred prior to ICF signature) or on the AE form in the eCRF (for findings presently occurring; events existing but unresolved prior to study intervention).

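### For completers, the by-treatment TEAE tables set 46–52 cladribine-label days against 26 placebo-label days per pair, and only the cladribine label contains the End of Study visit

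*SAP*

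**What the plan says.** SAP 15.1 defines the labels by sequence.

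- **Cladribine-placebo, cladribine label:** "Microgynon + Cladribine: From Day 9 of period 1, post-dose to Cladribine until Day 1 of period 2, pre-dose of Microgynon", and again "Microgynon + Cladribine: From Day 15 of period 2, post-dose to Cladribine until end of study".
- **Cladribine-placebo, placebo label:** "Microgynon + Placebo: From Day 9 of period 2, post-dose to Placebo until Day 15 of period 2, pre-dose of Cladribine".
- **Placebo-cladribine, placebo label:** "Microgynon + Placebo: From Day 9 of period 1, post-dose to Placebo until Day 1 of period 2, pre-dose of Microgynon".
- **Placebo-cladribine, cladribine label:** "Microgynon + Cladribine: From Day 9 of period 2, post-dose to Cladribine until end of study".

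SAP 15.1 and 15.1.1 then count subjects with at least one TEAE, and events, by treatment. The same counts are broken down by SOC and preferred term, severity and relationship. SAP 15.1 also announces summaries by sequence and period. It does not say which display is meant for comparing cladribine with placebo.

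Protocol 8.2.1 states: "Physical examination will be performed on the Screening Visit and on the End of Study Visit". The Schedule of Activities (protocol 1.3) adds laboratory tests, ECG and vital signs at the End of Study visit, 4–7 days after Day 21 of Period 2. Examination findings go on the AE form (protocol 8.2.1). Participants are questioned at each visit, and diagnostic findings can also give rise to AEs (protocol 8.3.2). On residency, protocol 4.1 says: "On Day 8 they will be hospitalized until discharge in the morning of Day 15".

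**The concern.** The safety and tolerability of co-administration is a secondary objective, and the TEAE tables serve it. Columns headed Microgynon + Cladribine and Microgynon + Placebo, placed side by side in a randomized crossover, invite a direct comparison.

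That comparison is fair only if the two labels give similar opportunity for an event to start and be recorded. Here the cladribine label is longer, and it alone ends in an examination visit. An excess of cladribine TEAEs could arise from this without any effect of the drug. A reader of the study report could not separate the two explanations from the by-treatment columns.

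**Working it through.** **Calendar check.** The protocol gives a total participation of 82 to 105 days (sections 4.1 and 8).

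- Shortest, with one Screening day: 1 + 28 + 28 + 21 + 4 = 82.
- Longest: 21 + 28 + 28 + 21 + 7 = 105.

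Both reproduce, and they place the End of Study visit on Period 2 Day 25 to 28. The stated 34 days between cladribine weeks (protocol 4.2) also reproduces: (28 + 15) − 9 = 34.

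**Label days.** Elapsed days = end day − start day, with Period 2 Day 1 counted as Day 29 of Period 1.

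| Sequence | Cladribine label | Placebo label |
|---|---|---|
| Cladribine-placebo | (29 − 9) + (25 to 28 − 15) = 20 + 10 to 13 = 30–33 | 15 − 9 = 6 |
| Placebo-cladribine | 25 to 28 − 9 = 16–19 | 29 − 9 = 20 |
| Pair (1:1) | 46–52 | 26 |

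Ratio: 46/26 = 1.77 to 52/26 = 2.00. If events started at a constant daily rate unrelated to treatment, the expected event count under cladribine would be about 1.8 to 2 times that under placebo.

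The ratio depends on how many completers each sequence has. Taking the protocol's 16 evaluable participants as an illustration:

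- Split 6:10 (cladribine-placebo : placebo-cladribine): placebo 6×6 + 10×20 = 236 days. Cladribine 6×30 + 10×16 = 340 to 6×33 + 10×19 = 388 days. Ratio 1.44–1.64.
- Split 10:6: placebo 10×6 + 6×20 = 180 days. Cladribine 10×30 + 6×16 = 396 to 10×33 + 6×19 = 444 days. Ratio 2.20–2.47.

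**Assessments per pair of completers, after dosing.** The Period 2 Day 9 laboratory draw is taken as pre-dose.

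| | Cladribine | Placebo |
|---|---|---|
| Physical examinations | 2 (End of Study) | 0 |
| Laboratory draws | 4 (two Day 14, two End of Study) | 2 (two Day 14) |
| Day 21 visits | 3 | 1 |
| In-house days (Day 9 to Day 15) | 12 | 12 |

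**Balanced alternatives.**

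- Period 1, Day 9 post-dose to Period 2 Day 1 pre-dose: 20 against 20 days, same residency and Day 21 visit, no End of Study visit for completers, and no earlier in-study cladribine in either group.
- Day 9 post-dose to Day 15 pre-dose of each period: 6 against 6 days per participant. In the cladribine-placebo sequence, however, the Period 2 placebo window opens (28 + 9) − 9 = 28 days after the first cladribine dose.

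**The case against.** **A balanced comparison is already planned.** The sequence-by-period summaries contain the Period 1 contrast. This stands and makes the remedy easy. But the SAP does not name it as the comparison, and SAP 15.1.1 describes its detailed tables as by treatment.

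**The tables are descriptive.** No test or decision rule compares the labels, and attributing an event to the last treatment taken is ordinary practice. This also stands. The primary PK analysis is untouched; the matter is how the safety tables will be read.

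**Not every End of Study finding becomes a cladribine TEAE.** A reader might infer that it does, for every participant. The documents do not support this. Labels follow onset, so an event found at the visit but dated earlier can fall elsewhere. Protocol Appendix 4 makes abnormal laboratory or ECG findings AEs only if they are symptomatic, lead to discontinuation or are considered medically important. Protocol 4.1 also gives early withdrawals the same assessments as far as feasible. A placebo-cladribine participant who leaves during her Period 1 placebo window would have them under placebo, and protocol 7.2 assumes 18–30% drop-out.

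**Placebo events are not shown to be over-detected.** A reader might infer this because in-house time is 12/26 = 46% of placebo-label days but only 12/46 to 12/52 = 26–23% of cladribine-label days. That gap comes wholly from the cladribine-placebo sequence: 6/6 = 100% against 6/30 to 6/33 = 20–18%. In placebo-cladribine it is slightly reversed: 6/20 = 30% against 6/16 to 6/19 = 38–32%. In-house days are equal, and the SAP tabulates counts, not rates per day. The lower share only reflects the extra cladribine-label days.

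**The matched window is not clean either.** Protocol 4.2 calls cladribine's action long-lasting, and Appendix 4 places the largest proportion with Grade 3 or 4 lymphopenia at 2 months after the first dose in each year. Delayed cladribine events could be counted as placebo in that window. This stands, so the window can be supportive only.

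**Conclusion.** The point holds for the by-treatment TEAE tables. Among completers at 1:1, the cladribine label covers 1.8 to 2 times as many days as the placebo label and alone contains the End of Study work-up. Both features favour finding events under cladribine, so these columns should not be read as a cladribine-placebo contrast.

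The figures rest on the protocol's visit days, equal numbers of completers per sequence, and an End of Study visit on Day 25–28. The size of the effect on actual TEAE counts cannot be derived from the documents. The examination part applies only to events with onset dated inside the label.

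The laboratory, vital-sign and ECG tables are not affected in this way, because SAP 15.3 to 15.5 give that visit its own label ("Follow-up: During follow-up/end of study period"). A reader might infer that End of Study AEs should be moved to a matching label. The documents do not support that step. The AE report content in protocol Appendix 4 lists onset and resolution dates but no detection date. In the cladribine-placebo sequence the visit is only 25 − 19 = 6 to 28 − 19 = 9 days after the last cladribine dose, so the move could take cladribine events out of the cladribine column.

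**What to change.** In SAP 15.1 and 15.1.1:

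1. Name the planned Period 1 columns, cladribine-placebo against placebo-cladribine from Day 9 post-dose to Period 2 Day 1 pre-dose, as the comparative AE display.
2. Add one supportive TEAE table restricted to onset from Day 9 post-dose to Day 15 pre-dose of each period, shown by sequence and period. Footnote that the cladribine-placebo Period 2 placebo window opens 28 days after the first cladribine dose and may contain delayed cladribine effects.
3. Keep the full-label tables, with a footnote giving the unequal window lengths and stating that, for completers, the End of Study visit falls only under cladribine.
4. Leave End of Study AEs in the cladribine label.

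The cost is SAP wording and one extra table, using the onset dates and times that SAP 15.1 already needs. The Period 1 display gives up the within-participant comparison. The matched window holds fewer events and may carry over cladribine effects, which is why neither display replaces the full-label tables.
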